6.0 Registration/Randomization Procedures

6.1 Registration Procedures

- 6.11 To register a patient, access the ACCRU web page at [REDACTED] go to Application section and click on “Registration” and enter the registration/randomization application. The registration/randomization application is available 24 hours a day, 7 days a week. Back up and/or system support contact information is available on the Web site. If unable to access the Web site, call the Academic and Community Cancer Research United (ACCRU) Registration Office at [REDACTED] the hours of 8 a.m. and 4:30 p.m. Central Time (Monday through Friday).

The instructions for the registration/randomization application are available on the above web page under Study Resources section, “Application Training”.

Prior to initiation of protocol study intervention, this process must be completed in its entirety and an ACCRU subject ID number must be available as noted in the instructions. It is the responsibility of the individual and institution registering the patient to confirm the process has been successfully completed prior to release of the study agent. Patient registration via the registration/randomization application can be confirmed in any of the following ways:

- Contact the ACCRU Registration Office [REDACTED]. If the patient was fully registered, the ACCRU Registration Office staff can access the information from the centralized database and confirm the registration.
- Refer to “Application Training” at [REDACTED]. Click on “Registration, Installation & Entry Instructions”.

6.12 Correlative Research

A mandatory correlative research component is part of this study, the patient will be automatically registered onto this component (see Sections 3.19 and 17.2).

- 6.13 Documentation of IRB approval must be on file in the Registration Office before an investigator may register any patients. Approvals should be uploaded using the online ACCRU Regulatory Management System (ARMS).

In addition to submitting initial IRB approval documents, ongoing IRB approval documentation must be on file (no less than annually) with ACCRU. Approvals should be uploaded using online ACCRU Regulatory Management Systems (ARMS) If the necessary documentation is not submitted in advance of attempting patient registration, the registration will not be accepted and the patient may not be enrolled in the protocol until the situation is resolved.

Submission of annual IRB approvals is required until the study has been closed through your IRB.

- 6.14 Prior to accepting the registration/randomization, the registration/randomization application will verify the following:
- IRB approval at the registering institution
 - Patient eligibility
 - Existence of a signed consent form
 - Existence of a signed authorization for use and disclosure of protected health information
- 6.15 At the time of registration, the following will be recorded:
- Patient has/has not given permission to store and use his/her tissue sample(s) for future research to learn about, prevent, or treat cancer.
 - Patient has/has not given permission to store and use his/her tissue sample(s) for future research to learn, prevent, or treat other health problems (for example: diabetes, Alzheimer's disease, or heart disease).
 - Patient has/has not given permission for ACCRU to give his/her tissue sample(s) to outside researchers.
- 6.16 Treatment cannot begin prior to randomization and must begin ≤ 14 days after randomization.
- 6.17 Pretreatment tests/procedures (see Section 4.0) must be completed within the guidelines specified on the test schedule.
- 6.18 All required baseline symptoms (see Section 10.52) must be documented and graded.
- 6.19a Treatment on this protocol must commence at an ACCRU institution under the supervision of a medical oncologist.
- 6.19b Study drug is available on site.
- 6.2 Randomization Procedures
- 6.21 The factors defined in Section 5.0, together with the registering membership, will be used as stratification factors.
- 6.22 After the patient has been registered into the study, the values of the stratification factors will be recorded, and the patient will be assigned to one of the treatment groups using the Pocock and Simon dynamic allocation procedure which balances the marginal distributions of the stratification factors between the treatment groups (Pocock-Simon ref – see below). The goal of the algorithm is to maintain arm balance with respect to the stratification factors (see Section 5.0).

In order to ensure that treatment assignment is not deterministic, a level of randomness has been added to the algorithm such that patients will be assigned to the arm that leads to less imbalance 90% of the time.

7.0 Protocol Treatment

7.1 Treatment Schedule - Use actual weight or estimated dry weight if fluid retention per institutional guidelines.

Arm	Agent	Dose Level	Route	Frequency	ReRx ¹
A	Pazopanib	800mg	PO	Once Daily	Every 28 days
	Ascorbic acid	1g/kg, titrate first 3 doses: 0.25, 0.5, and 0.75g/kg) in 1000ml sterile water** The maximum allowed dose is 100g.	IV (0.75-1g/min IV*)	3 times/ week (Mon/Wed/Fri) or (Tue/Thu/Sat) or	
B	Pazopanib	800mg	PO	Once Daily	

1. Cycles = 28 days

* Start infusion rate at 0.75g/minute. If no dizziness after 15 minutes the rate can be increased to 1 g/min. Infusion times are approximate (+/- 15 minutes) and may need to be adjusted based on patient tolerability.

**Exceptions during titration: First dose in 250 ml sterile water. Second dose in 500ml sterile water. If the maximum dose (based on the patient's weight) is less than 75 grams, then dose schedule is 25g, 50g, and then maximum calculated dose.

NOTE: Patients should be observed for 30 minutes after administration of ascorbic acid for at least the first 5 doses. Ascorbic acid infusions may not be given less than 24 hours apart. If patients miss one day of ascorbic acid IV, they can continue the following day. **If a patient misses more than 4 doses of ascorbic acid IV in any cycle, the local study doctor must consult with the Principal Investigator before the patient will be allowed to continue on study.**

7.2 Protocol treatment for Arm A consists of four 200mg tablets (800 mg) of pazopanib by mouth once each day plus IV ascorbic acid at 1g/kg given 3 times/week.

Protocol treatment for Arm B consists of four 200mg tablets (800 mg) of pazopanib by mouth once each day.

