Vitamin C has been used for many years as an oral anti-cancer agent. Although there were some studies that suggested benefit, oral ascorbic acid failed to demonstrate benefit in two randomized placebo controlled trials at the Mayo Clinic, [1, 2] after which mainstream oncologists discarded its role in cancer therapy. However, recent data on the pharmacokinetics of vitamin C and new understanding of its anti-cancer mechanism of action has led to resurgence in interest in exploring its potential in cancer therapy. These studies indicate that ascorbic acid at concentrations achieved only by the intravenous route functions as a pro-drug for hydrogen peroxide delivery to tissues and may have potential use in the treatment of cancer by induction of oxidative stress. [3-7] Phase 1 trials have demonstrated that intravenous ascorbate doses of up to 1-1.25g/kg are well tolerated with chemotherapy as well as targeted therapy, and there may be some anti-tumor activity.[8-10] It has also been shown to reduce the toxicity of chemotherapy. [11]

Clear cell RCC is an ideal model to test this hypothesis due to its characteristic high intratumoral iron content[12] and constitutionally active HIF pathway. We hypothesize that iron is an important component of the microenvironment to help ascorbate generate hydrogen peroxide; and it has already been shown that the constitutionally active HIF pathway renders ccRCC cells more susceptible to Vitamin C induced toxicity.[13] There have been case reports of excellent response of metastatic RCC with intravenous ascorbate.[14, 15] We propose testing the hypothesis in a randomized trial where patients will receive standard pazopanib either alone or with IV ascorbate.

[figure not shown]
Considering the impact of Mayo Clinic's studies on the use of vitamin C in cancer, we want to re-investigate the potential role of this agent in cancer therapy in the intravenous form, based on the accumulating evidence.

1.1 Mechanism 1

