High dose vitamin C is known to be well tolerated and to have negligible side effects in patients with preserved renal function [33, 34] and has been shown in many studies to improve the quality of life in advanced cancers.[35-37] Multiple phase I clinical trials of intravenous ascorbate in patients with advanced cancer measured plasma concentrations of ascorbate and evaluated clinical consequences. [33, 38, 39] In the study by Riordan and colleagues, patients were given continuous infusion of 0.15 to 0.7 g kg⁻¹ day⁻¹ for up to eight weeks; in the Hoffer study, ascorbate was administered three times per week at fixed doses of 0.4, 0.6, 0.9 and 1.5 g kg⁻¹; and in the most recent study by Monti et al., patients received 50, 75 and 100 g per infusion (three infusions per week) for 8 weeks with concomitant IV gemcitabine and oral erlotinib. In the Riordan study, ascorbate concentrations in serum during therapy ranged from 0.28 to 3.8 mM. In the Hoffer study, peak plasma ascorbate concentrations ranged from 2.4 to 26 mM. When 1.5 g kg⁻¹ was administered, plasma ascorbate concentrations exceeded 10 mM for \approx 4.5 h, levels that have been shown to induce cell killing in a variety of cancer cells [40, 41]. Finally in the Monti study, patients that received 100 g of ascorbate achieved peak plasma concentrations between 25 and 32 mM. All three trials demonstrated that high-dose intravenous ascorbate was well tolerated in cancer patients with normal renal function; the combination of ascorbate infusion with standard of care chemotherapies did not increase toxicity.

Since high dose intravenous vitamin C has been studied in combination with TKI sorafenib in hepatocellular carcinoma [42] and shown to be safe, we think it would be reasonable to conduct a phase 2 study with the therapeutic dose established in the phase 1 studies.

1.4 Proposal Hypotheses:

1. Combining high dose IV ascorbic acid with pazopanib for the first line treatment of clear cell metastatic ccRCC will result in improved treatment failure-free rate at 9 months, median progression-free survival, objective response rate, tolerance and duration on therapy compared to pazopanib alone.

Exploratory Hypotheses:

2. Patients with ccRCC having higher iron content in the tumor micro-environment, as determined by iron staining using Prussian blue reaction, will have a better response to the combination of IV ascorbic acid and pazopanib than those with lower iron content.

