15.2 Ascorbic Acid (Vitamin C, ASCOR®)

- 15.21 **Background:** Ascorbic acid (vitamin C), a water-soluble vitamin, is an essential coenzyme for collagen formation, tissue repair and synthesis of lipids and proteins. It acts both as a reducing agent and as an antioxidant and is necessary for many physiologic functions such as metabolism of iron and folic acid, resistance to infection, and preservation of blood vessel integrity.
- 15.22 **Formulation:** ASCOR® (ascorbic acid injection) 25,000 mg/50 mL (500 mg/mL) for intravenous use is a colorless to pale yellow, preservative-free, hypertonic, sterile, non-pyrogenic solution of ascorbic acid. [49] ASCOR must be diluted with an appropriate infusion solution (e.g. 5% Dextrose Injection, USP, Sterile Water for Injection, USP). Each ASCOR, 50 mL, Pharmacy Bulk Package vial contains 25,000 mg ascorbic acid, equivalent to 28,125 mg sodium ascorbate. Each mL of ASCOR contains 500 mg of ascorbic acid (equivalent to 562.5 mg of sodium ascorbate which amounts to 65 mg sodium/mL of ASCOR), 0.25 mg of edetate disodium, and water for injection. Sodium hydroxide and sodium bicarbonate are added for pH adjustment (pH range 5.6 to 6.6). It contains no bacteriostatic or antimicrobial agent.

15.23 Preparation and storage:

Penetrate each PBP vial closure **only one time** with a suitable sterile transfer device or dispensing set that allows measured dispensing of the contents. Given that pressure may develop within the vial during storage, exercise caution when withdrawing contents from the vial. Once the closure system has been penetrated, **complete all dispensing from the PBP vial within 4 hours**. Each dose **must be used immediately**. Discard unused portion.

Store vials in a refrigerator at 2°C to 8°C (36°F to 46°F). Protect vials from light and product has an expiration of 24 hours at room temperature. This product contains no preservative.

- 15.24 Administration:** Do not administer ASCOR as an undiluted intravenous injection. Administer 750mg – 1000 mg/minute as outlined in Section 7.1. Start infusion rate at 0.75g/minute. If no dizziness after 15 minutes the rate can be increased to 1 g/min. Infusion times are approx. (± 15 minutes) and may need to be adjusted based on patient tolerability. The maximum allowed dose is 100 g per infusion.

15.25 Pharmacokinetic information:

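### The low-weight titration exception in Section 7.1 has no lower limit, so below 50 kg the second ascorbic acid dose exceeds the patient's own calculated maximum

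*Combined protocol and SAP*

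**What the plan says.** Section 7.2 defines Arm A treatment as pazopanib "plus IV ascorbic acid at 1g/kg given 3 times/week". The table in Section 7.1 brings patients up to that dose in per-kg steps: "titrate first 3 doses: 0.25, 0.5, and 0.75g/kg". A footnote to the table makes an exception for lighter patients. When the maximum dose for the patient's weight "is less than 75 grams, then dose schedule is 25g, 50g, and then maximum calculated dose", the fixed gram steps apply instead.

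The only absolute ceiling is the one in Section 7.1, repeated in Section 15.24: "The maximum allowed dose is 100 g per infusion". Section 15.24 otherwise refers back to Section 7.1 for the rate. Sections 3.1 and 3.2 set no minimum body weight. The reductions in Sections 8.2 and 8.21 are triggered by adverse events and by creatinine, so they act after a dose has caused trouble and do not alter the titration schedule.

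**The concern.** The per-kg titration rises in three steps and stays below the 1 g/kg target throughout. The exception swaps in fixed gram amounts without checking that they remain below the target for the smallest patients. Once a patient's maximum is under 50 g, the sentence conflicts with itself: it names a maximum and also prescribes a step above it. Followed literally, the sequence overshoots at the second infusion and comes down at the third, which is not a titration towards target.

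The site then has no clean choice. Giving 50 g exceeds the protocol dose in Section 7.2; giving the calculated maximum departs from the listed gram schedule. Sites could differ, and either choice could be queried as a deviation. What is at stake is a single infusion above protocol dose in the lightest Arm A patients. Nothing in the documents suggests that this was intended.

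**Working it through.** **Inputs**

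- Target dose: 1 g/kg (Sections 7.1 and 7.2), using actual or estimated dry weight (Section 7.1).
- Absolute cap: 100 g per infusion (Sections 7.1 and 15.24).
- Exception: maximum below 75 g gives 25 g, 50 g, then the maximum (Section 7.1 footnote).
- Infusion rate: 0.75 to 1 g/min (Section 7.1).

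The plan states no derived figure to reproduce; the check applies its own rule.

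**Formulas**, with W the weight in kg:

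- Maximum M = min(1 × W, 100) g. Below 100 kg, M = W.
- If M < 75: doses are 25, 50, M.
- The second dose overshoots when 50 > M, that is, when W < 50. The threshold is exact.

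| Weight (kg) | Doses 1, 2, 3 (g) | Dose 1 (g/kg) | Dose 2 (g/kg) | Dose 2 minus maximum (g) |
|---|---|---|---|---|
| 35 | 25, 50, 35 | 25/35 = 0.71 | 50/35 = 1.43 | 15 |
| 40 | 25, 50, 40 | 25/40 = 0.63 | 50/40 = 1.25 | 10 |
| 45 | 25, 50, 45 | 25/45 = 0.56 | 50/45 = 1.11 | 5 |
| 49 | 25, 50, 49 | 25/49 = 0.51 | 50/49 = 1.02 | 1 |
| 50 | 25, 50, 50 | 25/50 = 0.50 | 50/50 = 1.00 | 0 |
| 60 | 25, 50, 60 | 25/60 = 0.42 | 50/60 = 0.83 | none (10 below) |

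From 50 kg up to 75 kg the second dose never exceeds the maximum and the sequence never falls, so the exception works there. Below 50 kg the first dose is still under target, so there is some titration; the defect is the one overshoot.

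**Against the experience the protocol cites**

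- Section 1.0 states that "intravenous ascorbate doses of up to 1-1.25g/kg are well tolerated with chemotherapy as well as targeted therapy". A 50 g dose passes 1.25 g/kg only below 50/1.25 = 40 kg.
- Section 1.3 describes a phase 1 trial in which "ascorbate was administered three times per week at fixed doses of 0.4, 0.6, 0.9 and 1.5 g" per kg. A 50 g dose passes 1.5 g/kg only below 50/1.5 = 33.3 kg.
- Section 1.3 also describes a trial in which "patients received 50, 75 and 100 g per infusion (three infusions per week) for 8 weeks". There 50 g was the lowest flat dose.

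**Infusion time.** At 1 and 0.75 g/min the excess adds 1 to 1.3 min at 49 kg, 5 to 6.7 min at 45 kg and 10 to 13.3 min at 40 kg. Section 7.1 says: "Infusion times are approximate (+/- 15 minutes) and may need to be adjusted based on patient tolerability". The extra time fits within that margin, so a longer infusion would not by itself draw attention to the overshoot. The margin concerns duration only and does not make the extra grams acceptable.

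**The case against.** The strongest reply is that the harm depends on the less natural reading. A maximum is ordinarily a ceiling and titration ordinarily climbs towards it, so a careful pharmacist would stop at 45 g for a 45 kg patient. That may well happen, but the footnote does not say it, and doing so means departing from an explicit gram schedule. A dosing instruction should not rely on the reader to correct it.

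A second reply is that the fixed steps have a practical basis. Section 15.22 describes vials of 25,000 mg, so 25 g and 50 g are one and two vials. This is an inference, though a reasonable one, and it explains why gram steps were used. It does not show that exceeding the maximum below 50 kg was meant.

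A third reply is that the infusion is well guarded. Section 7.1 requires 30 minutes of observation after at least the first five doses, a slow starting rate with a check for dizziness before any increase, and at least 24 hours between infusions. Section 4.0 has weekly chemistry for Arm A in Cycle 1, and Section 3 screens renal function. These safeguards limit the consequence and support a low rating. They do not correct the dose.

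The materiality argument stands in full: one infusion, possibly no patients, and no harm demonstrated from the documents. One qualification is that Section 1.3 ties good tolerance to normal renal function, and Section 15.27 notes renal failure after high doses in some patients with pre-existing renal disease. That does not raise the rating, but it is a reason not to leave an unintended overshoot in place.

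**Conclusion.** The concern holds, as a minor drafting error. Followed as written, every Arm A patient under 50 kg receives a second dose above the calculated maximum: by 1 g at 49 kg, 5 g at 45 kg and 10 g at 40 kg, with a lower third dose each time. No other section prevents it.

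The conclusion on the wording and the arithmetic is firm and rests only on the 1 g/kg target and the footnote as written. How many patients are affected cannot be said, because the documents give no weight distribution; it is probably few and could be none of the 41 planned eligible Arm A patients. The primary endpoint, randomization, sample size and analysis are not touched.

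**What to change.** Add one clause to the Section 7.1 footnote stating that no titration dose may exceed the patient's maximum calculated dose. The second dose becomes min(50, W) g:

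- 49 kg: 25, 49, 49 g
- 45 kg: 25, 45, 45 g
- 40 kg: 25, 40, 40 g
- 50 kg up to 75 kg: unchanged

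This follows the plan's own logic, since a 50 kg patient already reaches full dose at the second infusion. The diluent volumes can stay as they are. The cost is one line in an amendment or a clarification memo to sites.

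Using the table's per-kg steps below 50 kg would also remove the overshoot (11.25, 22.5, 33.75 g at 45 kg), but it would delay full dose to the fourth infusion and is not needed to correct the error.

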7.21 Dosage and Administration of Pazopanib

Administration of pazopanib with a high-fat or low-fat meal results in an approximately 2-fold increase in area under the plasma drug concentration curve (AUC) and maximum observed plasma drug concentration (C_{max}).

If a dose is missed, the subject should take the dose as soon as possible, but only if there are 12 or more hours remaining before the next dose is due. If the next dose is due in less than 12 hours, the subject should skip the missed dose and take the next dose as scheduled.

If vomiting occurs after taking pazopanib, the subject should not take a replacement dose on that day. The subject should resume taking pazopanib at the next scheduled dose on the following day. If vomiting persists, the subject should be instructed to notify the investigator.

As a general rule, if dose reduction of pazopanib is necessary, the dose should be reduced stepwise by 200 mg at each step, and the subject should be monitored for approximately 10 to 14 days at each dose level. If toxicity does not abate during this monitoring time, the medication may need to be interrupted and/or the dose further decreased with continued monitoring for an additional 10-14 days at each dose level, and so on.

If the toxicity has abated with reduction of the dose and dose re-escalation is considered safe by the investigator, the dose can then be increased step-wise back to the pre-event dose (in 200 mg increments, after monitoring for 10-14 days at each dose level to ensure that toxicity did not recur or worsen).

If a subject's treatment with pazopanib has been interrupted for more than 21 consecutive days, the local medicals doctor must contact the Study Principal Investigator to review the subject's condition in order to resume the treatment.

7.3 For this protocol, the patient must return to the consenting ACCRU institution for evaluation at least every 28 days during treatment

7.5 Administration of IV ascorbic acid by a non-study local medical doctor (LMD) is not allowed.

8.0 Dosage Modification Based on Adverse Events

8.1 Pazopanib

8.1.1 Pazopanib Dose Reduction Levels

Starting Dose	800 mg once daily
Dose Level -1	600 mg once daily
Dose Level -2	400 mg once daily

8.12 Dose Modifications for Pazopanib at Time of Treatment

→ → Use the NCI Common Terminology Criteria for Adverse Events (CTCAE) version 4.0* unless otherwise specified ← ←			
CTCAE System/Organ/Class (SOC)	ADVERSE EVENT	AGENT	ACTION**
BASED ON INTERVAL ADVERSE EVENT			
Investigations	Platelet count decreased Grade 3 or 4	Pazopanib	Omit until \leq Grade 2 then restart at next lower dose level. If no recovery to grade 2, discontinue
Investigations	
Prolongation of QTc Interval (If the QTc is prolonged, the ECG should be manually read to ensure accuracy of the reading. The values below refer to manually read ECGs.)
 
QTc \geq 480 < 500 msec
 
QTc \geq 500 msec
	Pazopanib	
Continue pazopanib; monitor as clinically indicated. Consider reducing Pazopanib dose to dose level 1 and gradually increase as tolerated. Recommend discontinuing any other QT prolonging agent in the patient's medication list.
 
Interrupt Pazopanib and discontinue any other QT prolonging agent in the patient's medication list. Recheck EKG in 1 week, If < 500msec, restart Pazopanib at dose level 2 with close monitoring. If recurrent/ refractory QTc > 500msec, discontinue pazopanib and continue follow-up per protocol.

Renal and urinary disorders	Creatinine \geq Grade 3	Pazopanib	Omit until < Grade 3 then restart at next lower dose level. If \geq Grade 3 recurs, reduce one dose level again until no dose can be given (see Section 8.2 regarding ascorbic acid dose reduction)

→ → Use the NCI Common Terminology Criteria for Adverse Events (CTCAE) version 4.0* unless otherwise specified ← ←			
CTCAE System/Organ/ Class (SOC)	ADVERSE EVENT	AGENT	ACTION**
	Proteinuria UPC <3 UPC ≥3 or 24-h urine protein ≥3g	Pazopanib	Continue pazopanib at the current dose; monitor as clinically indicated 1. Interrupt pazopanib. 2. Weekly UPC or 24-hr urine protein monitoring until UPC is <3 or 24-hr urine protein is <3 grams. Then restart pazopanib dose-reduced by 200 mg. 3. If UPC ≥3 or 24-h urine protein ≥3g recurs, repeat steps 1 and 2. 4. If UPC ≥3 or 24-hr urine protein ≥3 recurs and the pazopanib dose can no longer be reduced, discontinue pazopanib and continue follow-up per protocol.

→ → Use the NCI Common Terminology Criteria for Adverse Events (CTCAE) version 4.0* unless otherwise specified ← ←				
CTCAE System/Organ/Class (SOC)	ADVERSE EVENT	AGENT	ACTION**	
Vascular disorders	Thromboembolic event	Pazopanib	
Continue pazopanib at the current dose; monitor as clinically indicated
	
	DVT/PE			
	Grade 2			
	Grade 3			
Omit and initiate anticoagulant. Restart at reduced dose if
 
 • Subject must have been treated at desired level of anticoagulation for at least 1 week • No Grade 3 or 4 or clinically significant Grade 2, hemorrhagic events have occurred while on anticoagulation treatment. 
Note: When treating with warfarin, INR S/B monitored within 3 to 5 days after any change in pazopanib dosing and then at least weekly until INR is stable. The dose of warfarin may need to be adjusted to maintain the desired level of anticoagulation.

	Grade 4			Discontinue pazopanib
Arterial Thrombosis/Ischemia Any Grade	Discontinue pazopanib			
	Thrombocytopenia: Investigate and document underlying cause		
Continue pazopanib with current dose; monitor as clinically indicated.
 
Step 1. Interrupt pazopanib until toxicity resolves to ≤ Grade 2. Step 2. Restart pazopanib dose-reduced by 200 mg and monitor as clinically indicated.
 
If no recovery to ≤ Grade 2 or recurrent Grade 3 or 4 thrombocytopenia, discontinue Pazopanib and follow-up per protocol.
	
	Grade 1 or 2			
	Grade 3 or 4			

→ → Use the NCI Common Terminology Criteria for Adverse Events (CTCAE) version 4.0* unless otherwise specified ← ←			
CTCAE System/Organ/Class (SOC)	ADVERSE EVENT	AGENT	ACTION**
Vascular disorders	
Hypertension (Scenario A)
 
Asymptomatic and persistent^d SBP of ≥ 140 and < 160 mmHg, or DBP ≥ 90 and < 100 mmHg,
 
Or
 
Clinically significant increase in DBP of 20 mmHg (but still below 110 mmHg).
	Pazopanib	
 • Continue pazopanib treatment at the current dose • Adjust current or initiate new antihypertensive medication • Titrate antihypertensive medication(s) during the next 2 weeks as indicated to achieve well-controlled BP • If BP is not well controlled within 2 weeks, consider referral to a specialist and go to scenario (B).
	
(Scenario B)
 
Asymptomatic SBP ≥ 160 mmHg, or DBP ≥ 100 mmHg,
 
Or
 
Failure to achieve well-controlled BP within 2 weeks in Scenario A
	Pazopanib	
 • Interrupt pazopanib treatment if clinically indicated • Adjust current or initiate new antihypertensive medication(s) • Titrate antihypertensive medication(s) during the next 2 weeks as indicated to achieve well-controlled BP • Once BP is well controlled^e, restart pazopanib treatment reduced by one dose level

→ → Use the NCI Common Terminology Criteria for Adverse Events (CTCAE) version 4.0* unless otherwise specified ← ←			
CTCAE System/Organ/Class (SOC)	ADVERSE EVENT	AGENT	ACTION**
	Symptomatic ^f hypertension or Persistent ^g SBP ≥160 mmHg, or DBP ≥100 mmHg, despite antihypertensive medication and dose reduction of study treatment	Pazopanib	
 • Interrupt pazopanib treatment • Adjust current or initiate new antihypertensive medication(s) • Titrate antihypertensive medication during the next 2 weeks as indicated to achieve well-controlled BP • Referral to a specialist for further evaluation and follow-up is recommended Once BP is well controlled, restart pazopanib treatment reduced by one dose level
	Refractory hypertension unresponsive to above interventions.	Pazopanib	
 • Permanently discontinue pazopanib treatment • Continue follow-up per protocol.

→ → Use the NCI Common Terminology Criteria for Adverse Events (CTCAE) version 4.0* unless otherwise specified ← ←				
CTCAE System/Organ/Class (SOC)	ADVERSE EVENT	AGENT	ACTION**	
Cardiac Disorders	LVEF-drop (%) or CTCAE grade	Pazopanib	
 • Interrupt pazopanib study treatment and repeat ECHO within 2 weeks^b and monitor and control BP. • If the LVEF recovers within 4 weeks (defined as LVEF \geqLLN and absolute decrease \leq10% compared to baseline) 
 -Restart study treatment^f reduced by one dose level (Contact ACCRU if there are any questions prior to restarting) -Repeat ECHO 2 , 4 , 8 and 12 weeks after re-start; monitor BP; continue in intervals of 12 weeks thereafter • If repeat LVEF does not recover within 4 weeks 
 -Consult with cardiologist -Permanently discontinue pazopanib treatment Repeat ECHO after 2, 4, 8, 12, and 16 weeks or until resolution. (Contact ACCRU if there are any questions) 	
	Asymptomatic: Absolute decrease of >10% in LVEF compared to baseline and ejection fraction below the institution's LLN			Pazopanib
	Or LVEF drop >15% from baseline regardless of whether value is below institution's LLN.			
Symptomatic ^c Grade 3: resting LVEF 39-20% or >20% absolute reduction from baseline	Pazopanib	
 • Permanently discontinue pazopanib treatment • Consult with cardiologist • Repeat ECHO after 2, 4, 8, 12, and 16 weeks or until resolution 		
Symptomatic ^c Grade 4: resting LVEF <20%				

→ → Use the NCI Common Terminology Criteria for Adverse Events (CTCAE) version 4.0* unless otherwise specified ← ←			
CTCAE System/Organ/Class (SOC)	ADVERSE EVENT	AGENT	ACTION**
Gastrointestinal disorders	GI bleed Grade 2	Pazopanib	Interrupt pazopanib, restart at dose level 2 when bleeding has resolved and gradually titrate up as tolerated.
	Grade 3 or Grade 4		Discontinue Pazopanib
Respiratory, thoracic and mediastinal disorders	Pulmonary bleed Grade 1	Pazopanib	For Grade I hemoptysis, continue pazopanib at the current dose; monitor as clinically indicated.
	Grade 2		Interrupt pazopanib, restart at dose level 2 when bleeding has resolved and gradually titrate up as tolerated.
	Grade 3 or 4 or Recurrent ≥ Grade 2 event after dose interruption/reduction.		Discontinue pazopanib and continue with follow-up per protocol.
Dermatology/ Skin	Dermatitis Grade 2 skin changes w/pain, limiting ADL's	Pazopanib	Omit until ≤ Grade 1, then restart at next lower dose level. If recurrent, reduce by another dose level or discontinue
	Grade3 severe skin changes w/pain Limiting self-care ADL's		Discontinue pazopanib

→ → Use the NCI Common Terminology Criteria for Adverse Events (CTCAE) version 4.0* unless otherwise specified ← ←			
CTCAE System/Organ/Class (SOC)	ADVERSE EVENT	AGENT	ACTION**
Skin and subcutaneous tissue disorders	
Palmar-plantar Erythrodysesthesia Syndrome
 
Grade 1 Minimal skin changes or dermatitis without pain (erythema, oedema, hyperkeratosis)
 
Grade 2 Skin changes with pain; limiting instrumental activities of daily living (ADLs) (peeling, blisters, oedema, bleed, hyperkeratosis)
 
Grade 3 Severe skin changes with pain and limiting self-care
	Pazopanib	
Continue pazopanib at present dose
 
 1. Hold pazopanib 2. Treat as clinically appropriate 3. Upon resolution to Level 1 or better restart pazopanib with a dose reduction to dose level -1 (if it was a full dose [800mg]) or one dose lower than the patient was receiving prior to developing the skin changes. 4. If recurrent consider a further dose reduction by 1 dose level until dose level -2. If patient has a Grade 2 toxicity on dose level -2, then consider stopping the drug. 
Discontinue pazopanib

Blood and lymphatic system disorders	Anemia	Pazopanib	No specific dose reduction rules are indicated for anemia unless due to hemorrhage or bleeding as noted above.
All Other	
Grade 1
 
Grade 2 or 3, if clinically significant
 
Grade 4
	Pazopanib	
Continue pazopanib; monitor as clinically indicated.
 
Omit until \leq Grade 1 Restart pazopanib dose-reduced by 200 mg (1 dose level) and monitor as clinically indicated.
 
Discontinue Pazopanib and continue follow-up per protocol.

* Located at [REDACTED]

- ** Use the following to describe actions in the Action column:
- Omit = Treatment is not given for this cycle
 - Hold/Delay = Treatment can be made up as part of this cycle
 - Discontinue = Treatment is totally stopped

- a. AEs are graded according to NCI Common Terminology Criteria for Adverse Events v4.0 (NCI CTCAE v4)
- b. If ECHO does not show LVEF recovery after 2 weeks, repeat ECHO 2 weeks later.
- c. Symptoms may include: dyspnea, orthopnea, and other signs and symptoms of pulmonary congestion and edema.
- d. Hypertension detected in two separate readings during up to three consecutive visits
- e. Well-controlled blood pressure defined as SBP <140 mm Hg and DBP <90 mm Hg in two separate readings during up to three consecutive visits.
- f. Symptomatic hypertension defined as hypertension aggravated by symptoms (e.g., headache, light-headedness, vertigo, tinnitus, episodes of fainting) that resolve after the blood pressure is controlled within the normal range.
- g. Persistent hypertension is defined as asymptomatic hypertension after initially successful anti-hypertensive intervention.

